#### **Synopsis**

#### **Protocol Title:**

Sodium nitrite administration at the time of lung organ procurement and transplantation to minimize the risk of pulmonary graft dysfunction

Study Site: University of Pittsburgh Medical Center

#### Phase of Development: Phase II A

#### **Objectives:**

Primary Objective(s):

 To evaluate the safety of Sodium Nitrite infusion into the procured lungs and lung transplant recipient as reflected in blood mean arterial pressure and methemoglobin levels.

Secondary Objectives:

- To evaluate the efficacy of Sodium Nitrite infusion into the procured lungs and the lung transplant recipient in the prevention of grade 2-3 Primary Graft Dysfunction.
- To evaluate the efficacy of Sodium Nitrite infusion into the procured lungs and the lung transplant recipient in the prevention of delayed allograft complications including the incidence of acute rejection and BOS
- To identify the pharmacokinetic relationship of Sodium Nitrite and

metabolism of sodium nitrite in lung transplant recipients using blood sampling measures before and after drug exposure (will measure levels of plasma and whole blood nitrite, plasma nitrate, red cell iron-nitrosylhemoglobin, S-nitroso-hemoglobin and methemoglobin).

Statement of Primary Efficacy Hypothesis and Primary Analysis:

The administration of Sodium Nitrite at the time of organ procurement and transplantation will be safe and significantly reduce the rate of Primary Graft Dysfunction in patients undergoing lung transplantation.

**Planned Sample Size**: A total of 8 subjects will be enrolled into the protocol. Recruitment is expected to continue for six months.

Study Design: Phase IIA observational non-randomized cohort.

**Diagnosis and Key Patient Selection Criteria:** Males or females greater than 18 years of age or older undergoing lung transplantation.

**Treatments:** Sodium Nitrite infusion to the donor lungs and the lung transplant recipient.

## 1 Abstract

While increasing numbers of patients with advanced lung disease are candidates for lung transplantation, the short- and long-term outcomes are severely compromised by graft dysfunction, primarily in the form of organ rejection. The earliest manifestation of lung allograft dysfunction, termed primary graft dysfunction (PGD), represents a form of ischemia-reperfusion acute lung injury, and occurs in its severest form (Grade 3) in from 10 to 35% of lung transplant recipients . PGD is the primary cause of early morbidity and mortality after transplantation and is strongly associated with the late development of chronic lung rejection or Bronchiolitis Obliterans Syndrome (BOS) . Early graft dysfunction contributes significantly to the suboptimal outcomes of lung transplantation and to the failure of lung transplant recipients to achieve five-year survival rates comparable to patients who receive other solid organs such as the heart and liver. The risk of PGD further limits the time that lungs can be stored ex-vivo, therefore restricting the pool of available donors. A critical advance in the prevention of both early and late lung allograft dysfunction will occur if PGD can be successfully prevented or minimized.

In this study, we propose to test the hypothesis that administration of Sodium Nitrite to donor lungs and lung transplant recipients at the time of transplantation will be safe and will reduce the incidence of grades 2 and 3 PGD, thereby improving clinical outcomes with minimal toxicity.

Sodium Nitrite will be obtained from a commercial preparation (Hope Pharmaceuticals, Sodium Nitrite Injection USP (30mg/mL) NDC Number 60267-079-02) and the UPMC Pharmacy will prepare the formulations, which will be infused at three time points. First it will be infused into the preservation solution bag at the time of organ procurement from the donor, then to the allograft at the time of transplantation, and finally as a direct infusion into the organ recipient.

We plan to enroll total of 8 subjects undergoing lung transplantation for this Phase IIA observational non-randomized pilot investigation to evaluate the safety, efficacy, and pharmacokinetics of Sodium Nitrite administration when administered to the procured lung and lung transplant recipient, for the prevention of Primary Graft Dysfunction (PGD). It is anticipated that positive results from this trial lead to a larger clinical investigation of Sodium Nitrite administration directed at producing a reduction in PGD and perhaps secondary obliterative bronchiolitis; and will potentially allow for extended organ storage, extended use of more marginal organs, and more effective use of Donation after Cardiac Death (DCD) organs which undergo combination of warm and cold ischemia for organ procurement.

## 2 Objective, Specific Aims and Endpoints

#### 2.1 Objective

The objective of this Phase IIA observational non-randomized pilot investigation is to evaluate the safety, efficacy, and pharmacokinetics of Sodium Nitrite administration when administered to the procured lung and lung transplant recipient, for the prevention of Primary Graft Dysfunction (PGD).

#### 2.2 Hypothesis

Administration of Sodium Nitrite to donor lungs and lung transplant recipients at the time of transplantation will be safe and will reduce the incidence of grades 2 and 3 PGD, thereby improving clinical outcomes with minimal toxicity.

#### 2.3 Specific Aims

The specific aims of this study are:

#### Primary Objective(s):

• To evaluate the safety of Sodium Nitrite infusion into the procured lungs and the lung transplant recipient as reflected in blood mean arterial pressure and methemoglobin levels.

#### Secondary Objectives:

- To evaluate the efficacy of Sodium Nitrite infusion into the procured lungs and the lung transplant recipient in the prevention of grade 2-3 primary graft dysfunction.
- To evaluate the efficacy of Sodium Nitrite infusion into the procured lungs and the lung transplant recipient in the prevention of delayed allograft complications including the incidence of acute rejection and BOS.
- To identify the pharmacokinetic relationship of Sodium Nitrite and metabolism of sodium nitrite in lung transplant recipients using blood sampling measures **before and after** drug exposure (levels of plasma and whole blood nitrite, plasma nitrate, red cell ironnitrosyl-hemoglobin, S-nitroso-hemoglobin and methemoglobin will be measured).

#### 2.4 Endpoints

#### Primary Endpoints Analysis

- The primary endpoint for the safety of Sodium Nitrite administration will be assessed by measurement of methemoglobin levels and mean arterial pressure during the nitrite infusion in the transplant recipient.
- The primary endpoint for the efficacy of Sodium Nitrite infusion will be the incidence of grades 2 and 3 PGD using the International Society for Heart and lung transplant (ISHLT) criteria for PGD based upon the worst value obtained over the initial 72 hours post lung reperfusion (T0-72).

#### Secondary Endpoint Analysis

- Secondary endpoints for efficacy will include AUC curves for the oxygenation index during the initial 72 hours post transplantation, ventilator free days, intensive care free days and hospital days.
- The secondary endpoints for the prevention of Bronchiolitis Obliterans(BO) will be captured for up to 12-months following lung transplantation and include clinically

indicated spirometric and lung volume assessments of lung function performed as an indicator of Bronchiolitis Obliterans Syndrome (BOS), and evidence of pathological rejection by surveillance transbronchial lung biopsies.

#### 3 Background and Rationale

While increasing numbers of patients with advanced lung disease are candidates for lung transplantation, the short- and long-term outcomes are severely compromised by graft dysfunction, primarily in the form of organ rejection. The earliest manifestation of lung allograft dysfunction, termed primary graft dysfunction (PGD), represents a form of ischemia-reperfusion acute lung injury, and occurs in its severest form (Grade 3) ranging from 10 to 35% of lung transplant recipients 1-6. PGD is the primary cause of early morbidity and mortality after transplantation and is strongly associated with the late development of chronic lung rejection or bronchiolitis obliterans syndrome (BOS) 7-9. Early graft dysfunction contributes significantly to the suboptimal outcomes of lung transplantation and to the failure of lung transplant recipients to achieve five-year survival rates comparable to patients who receive other solid organs such as the heart and liver. The risk of PGD further limits the time that lungs can be stored ex-vivo, therefore restricting the pool of available donors. A critical advance in the prevention of both early and late lung allograft dysfunction will occur if PGD can be successfully prevented or minimized.

The International Society for Heart and Lung Transplant (ISHLT) guidelines have provided a standardized definition for PGD based on the PaO2/FiO2 (P/F) ratio and the presence of chest radiograph infiltrates assessed within the first 72 hours following transplantation . The frequency of PGD has varied in published reports within the range of 70-80% as outlined in Table 1.

Table 1: Frequency of Reported PGD by Grade and Definition Using a Component of						
ISHLI Criteria						
Reference	Time (N)	Definition	PGD 0 (%)	PGD 1 (%)	PGD 2 (%)	PGD 3 (%)
Prekker 2005 (5)	1992-2004 (402)	T (0-48)		38%	28%	34%
Bobadilla 2008 (1)	1999-2008 (33)	Т72				30%
Daud * 2007 (7)	1998-2004 ( 334)	то	19%	39%	21%	21%

Table 1: Frequency of Reported PGD by Grade and Definition Using a Component of							
ISHLT Criteria							
Reference	Time (N)	Definition	PGD 0 (%)	PGD 1 (%)	PGD 2 (%)	PGD 3 (%)	
Huang * 2008 (3)	1998-2004 (334)	T48	17%	65%	8%	9%	
Christie 2009 (11)	2003-2007 (317)	Т24				20%	
Pittsburgh, unpublished	2003-2004 (76)	T (0-72)	21%	34%	20%	25%	

+ Grouped 0-1 into Group 1. Did not include radiographic scoring component

\* Identical cohort analyzed at different time points

PGD grade 3 has been associated with a 90-day mortality of 16.2% in comparison to a mortality of 9.5% for subjects with PGD Grades 0-1. However, the prognostic significance of PGD extends well beyond the immediate post-operative period. Grade 3 PGD has been associated with a more rapid decline in post-operative pulmonary function and the late development of bronchiolitis obliterans syndrome (BOS). These data suggest that new approaches to reduce PGD are fundamental to improving the morbidity and mortality in lung transplant recipients.

4.3.1 Complex Interaction of Donor and Recipient Risk Factors Contributing to Primary Graft Dysfunction

Using the standardized definition for PGD, numerous donor, recipient, and treatment variables have been identified as potential clinical risk factors for the development of PGD . These reported associations remain limited by the lack of multicenter, prospective, observational studies using consistent procurement techniques. Despite this limitation, both single center and registry reviews have suggested that variables such as donor age , prolonged ischemia time , recipient pulmonary hypertension , recipient diagnosis , and donor requirement for blood transfusion , may all be independent risk factors for PGD.

4.3.2 Rationale for the Investigation of Nitrite Therapy in PGD

Sodium Nitrite has been shown to limit ischemia-reperfusion injury and myocardial infarction. Nitrite is a potent cytoprotective agent, with its optimal dose (48 nmol - which raises murine plasma nitrite concentration to  $10 \mu$ M) decreasing infarct size by 50-70% in the heart, liver and

**Figure 1**: Inhibition of mitochondrial ROS and cytochrome C release by nitrite during anoxia and reoxygenation. A) nitrite inhibits complex I activity; B) decreases ROS generation; C) decreases permeability pore opening (measured as mitochondrial swelling; and D) Western blot for cytochrome c remaining in the mitochondria. Shiva et al. J. Ex. Med 2008.

brain of respective animal models . This cytoprotective effect of nitrite after ischemia/reperfusion (IR) has now been observed by a number of groups and in a number of organs/models. Although this cytoprotection has been shown to be dependent on the formation of nitric oxide (NO), it is independent of endothelial NO synthase. Recent data have also demonstrated that dietary nitrite supplementation can increase plasma and tissue levels of nitrite, and these increased levels can protect against IR injury in the heart and liver . The mechanism of bioactivation of nitrite in the ischemic organ is the subject of intense current study, with groups proposing a central role for xanthine oxidoreductase , mitochondrial enzymes , NO synthase , as well as nonenzymatic acidic disproportionation .

The mechanism of nitrite cytoprotective effect involves the inhibition of mitochondrial respiration and decreased ROS at reperfusion. Nitrite appears to be mitochondrially-targeted and able to modulate mitochondrial reactive oxygen species (ROS) generation . We have demonstrated that nitrite dose dependently S-nitrosates and inhibits mitochondrial complex I in vivo models of IR as well as in vitro models of anoxia/reoxygenation (Figure 1).

This post-translational modification decreases electron transfer through complex I, which effectively decreases ROS generation upon reperfusion and prevents protein oxidation and loss of function . Similar to other complex I inhibitors, the nitrite dependent S-nitrosation of complex I reduces reperfusion reactive oxygen species formation and oxidative damage to the mitochondria (indicated by a reduction in aconitase oxidation). In addition, nitrite prevents

opening of the mitochondrial permeability transition pore and the release of cytochrome c from the mitochondria in response to calcium, an effect similar to that of cyclosporine on mitochondrial function

#### 4.3.3 NO And Nitrite Regulate Cellular Apoptosis

The mitochondrial apoptotic pathway is initiated by opening of the mitochondrial permeability transition pore and cytochrome c of mitochondrial ROS and cytochrome C release in a process inhibited by nitrite (Figure 1) and regulated by the pro- and anti-apoptotic proteins bax and bcl-2. This pathway drives the activation of caspase 9 and assembly of the apoptosome, which leads to the eventual activation of caspase 3. This pathway plays a central role in the cytotoxicity of ischemia and reperfusion, as demonstrated by studies in which inhibiting caspase 9 or overexpressing the anti-apoptotic protein bcl-2, significantly decreases infarct size in myocardial infarction models.

At low concentrations, NO regulates several steps in the apoptotic pathway including inhibiting the release of cytochrome C  and the activation of caspases 9 and 3 , and maintaining levels of the anti-apoptotic protein bcl-2 .

Consistent with these data, nitrite inhibits caspase 3 activation (Figure 2).

**Figure 2**: Caspase 3 activity in wild type mice after I/R with or without nitrite treatment.

## 4.3.4 Sodium Nitrite Therapy as the Most Promising Pilot Trial to Model in The Treatment Of PGD

Accumulating evidence suggests that the ubiquitous anion, nitrite (NO2-), is a physiological signaling molecule, with roles in intravascular endocrine nitric oxide (NO) transport, hypoxic vasodilatation, and cellular cytoprotection .

Numerous pre-clinical studies in mice, rats, dogs, sheep and primates have shown that nitrite has both vasodilatory and tissue protective effects in models of ischemia-reperfusion injury to the central nervous system, liver, kidney, heart and lung . Additionally, recent pre-clinical studies, as outlined below, now indicate that nitrite has potent effects at reducing primary graft dysfunction and late rejection after lung and heart transplantation . Most importantly, phase I-II studies of nitrite infusion, at doses much higher than the 40 mg dose planned for this trial, have been completed in more than 80 human volunteers and patients with sickle cell disease with no observed toxicity . In collaborative studies at the University of Pittsburgh with the Department of Surgery and the Starzl Transplantation Institute, we have evaluated Sodium Nitrite in rat models of lung transplantation and heart transplantation. These studies show that nitrite not only potently inhibits early ischemia and reperfusion injury but also prevents down-stream allograph rejection.

Heart Transplantation Models: In these studies, fully allogeneic heterotopic heart transplantation was performed in Lewis (LEW) to Brown Norway (BN) rats. Animals were all given tacrolimus therapy, and either a regular diet or a low nitrite/nitrate chow validated in [name] laboratory or the low chow but with water containing nitrite (50 mg/L) for 120 days, beginning 7 days before transplant. Serum nitrite/nitrate levels were significantly higher in animals given nitrite water for 30 days, and lower in the animals fed with low nitrite/nitrate diet than those in animals who received standard diet. Supplementation of drinking water with nitrite enhanced heart graft survival to a median of >120 days from 49.5 days in animals fed a standard diet. In contrast, the low nitrite/nitrate diet led to nitrite and nitrate insufficiency and resulted in significantly earlier rejection of allografts (30.5 days). These data demonstrate that nitrite supplementation is significantly effective in preventing development of heart allograft rejection in a relevant pre-clinical model .

**Figure 3:** Increase in oxygenation after lung transplantation (LTx) in mice receiving nitrite in both the lung preservation solution (LPD) and IV at the time of reperfusion. Lung transplantation models: In these studies, orthotropic left lung transplantation (LTx) was performed syngeneic rats. Grafts were preserved with or without Sodium Nitrite (10  $\mu$ M) in the cold storage

solution at 4°C for 6 hours.

Groups of recipients also received Sodium Nitrite at a

dose of 480 nmoles intravenously 5 minutes before graft reperfusion to target a plasma concentration of 10 µM. Graft function, as measured by the pulmonary vein PaO2 while breathing 100% oxygen and inflammatory lung injury were assessed 2 hours after transplantation.

We found that oxygenation was significantly higher in animals receiving Sodium Nitrite in both the preservation solution and given to the recipient compared to those in the control group (Figure 3; 234±53 vs 99±18 mm Hg; P<0.05). In contrast, nitrate did not alter gas exchange.

The increase of graft mRNA for IL-6, IL-1 $\beta$ , TNF- $\alpha$ , iNOS, and COX-2 in the control group was markedly inhibited in nitrite group. Lung myeloperoxidase activity, lung wet to dry weights and histological evidence of edema and cellular inflammation were all significantly reduced with nitrite treatment.

## 4 Significance

It is anticipated that positive results in this trial will lead to a larger clinical investigation of Sodium Nitrite administration directed at producing a reduction in PGD, and perhaps secondary obliterative bronchiolitis; and will potentially allow for extended organ storage, extended use of more marginal organs, and more effective use of Donation after Cardiac Death (DCD) organs which undergo combination warm and cold ischemia for organ procurement.

## 5 Study Design and Methods

#### 5.1 Overview

This is a Phase IIA observational nonrandomized pilot investigation to evaluate the safety and efficacy of Sodium Nitrite administration for the reduction of PGD in patients undergoing lung transplant. The study will enroll 8 subjects, undergoing lung transplant at the University of Pittsburgh Medical Center (UPMC).

#### 5.2 Study Time Line

We propose to enroll eight patients over a 6-month interval.

#### 5.3 Screening Procedures

Patients with end stage lung disease who are deemed eligible for placement on the lung transplant waiting list will be eligible for participation and written informed consent will be obtained at the time of their listing for lung transplantation. The medical records of the lung transplant patients will be reviewed for eligibility criteria by the PI and other Co- Investigators who by virtue of their role as a clinician already have the knowledge of and access to the patients' identifiable medical information. Subjects will be approached for consent after the decision has been reached to place the subject on the waiting list. After enrollment and prior to transplantation, blood will be drawn for baseline studies that include complete blood count (CBC), chemistry profile; and for storage to allow for subsequent exploratory PBMC gene expression profiling and proteomics which would include evaluation of IL6, IL $\beta$ , TNF-a, iNOS and COX-2.

#### 5.4 Study Drug Preparation

The Sodium Nitrite will be obtained from a commercially available, FDA-approved preparation (Hope Pharmaceuticals, Sodium Nitrite Injection USP (30mg/mL) NDC Number 60267-079-02) and the UPMC Pharmacy will prepare the formulations for this clinical study.

To minimize waste of study drug, the UPMC Pharmacy will prepare Sodium Nitrite as two stock solutions in syringes. The first stock solution will be a 12 mL (0.16mg/mL) stock solution to be used in the Perfadex preservation solution and the pneumoplegia solutions. The second stock solution will be 1.33 mL (30 mg/mL) stock solution to be used in the preparation of a 40 mg Sodium Nitrite infusion is normal saline. The stock solutions in syringe will be prepared from Hope Pharmaceuticals Sodium Nitrite Injection, USP. The stock solutions is syringe will be frozen for long term storage to be used as needed as enrollment progresses.

A specifically labeled frozen syringe of prepared stock Sodium Nitrite solution (12 mL, 0.16 mg/mL) will be available for the addition to the 2.8 L Perfadex bag. Once thawed, the addition of the 12 mL contents of the syringe will achieve a final concentration of 0.69 mg/L of solution (i.e., 10 uMolar or 1.93 mg for each 2.8 liter bag. Thawed syringes that are not used will be discarded.

An initial 1I bag of Perfadex administered to the donor organ will not include the addition of Sodium Nitrite.

#### Organ Implantation Prior To Reperfusion

A specifically labeled frozen syringe of prepared stock Sodium Nitrite solution (12 mL, 0.16 mg/mL) will be available to the OR at the time of lung transplantation. Once thawed, the Sodium Nitrite will be added to the pneumoplegia solution to achieve a final concentration of 0.69 mg/L (10 uMolar), Thawed syringes that are not used will be discarded. The pneumoplegia solution (see Appendix C) is prepared by the UPMC Pharmacy and the Sodium Nitrite will be added immediately prior to the infusion of the pneumoplegia solution into the donor lung.

#### Organ Reperfusion to Recipient

A specifically labeled frozen syringe of prepared stock Sodium Nitrite solution (1.33 mL, 30 mg/,L) will used by the UPMC pharmacy to prepare a 40 mg Sodium Nitrite in a 250 ML infusion

bag of normal saline (i.e., 0.16 mg/mL) The entire volume of this bag will be used to administer to the patient at the time of Organ Perfusion.

#### 5.5 Study Drug Intervention

Sodium Nitrite will be administered to the donated lung at the time of procurement and to the lung transplant recipient at the time of reperfusion.

#### Organ Procurement from the Donor

Consistent with current practice, the initial liter of antegrade flush of the donor lung with Perfadex includes the addition of prostaglandin and nitroglycerin to a 1L bag of the preservation solution. This initial liter of solution WILL NOT include the addition of Sodium Nitrite. Subsequent to this initial liter, any additional preservation solution (Perfadex) will be provided in 2.8 Liter bags only and will include the addition of Sodium Nitrite for injection to achieve a final concentration of 0.69 mg/mL (10 uMolar). Other additives to the preservation solution will include THAM and calcium chloride consistent with local practice. The Sodium Nitrite will be added prior to the infusion of the preservation solution. The actual volume of solution used for both antegrade (PA to PV) and retrograde (PV to PA) flush will be determined by the surgical team directing the procurement and recorded for the purpose of this study. A member of the study team will be present for monitoring of this procedure.

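### Sections 5.4 and 5.5 give the 2.8 L Perfadex bag two sodium nitrite strengths that differ 1000-fold (0.69 mg/L and 0.69 mg/mL)

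*Combined protocol and SAP*

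**What the plan says.** Two sections specify the sodium nitrite content of the 2.8 L Perfadex bag.

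- **Section 5.5, Organ Procurement from the Donor (administration).** After a first litre without nitrite, all further Perfadex comes in 2.8 L bags, and the solution "will include the addition of Sodium Nitrite for injection to achieve a final concentration of 0.69 mg/mL (10 uMolar"). No syringe, added volume or mass per bag is given.
- **Section 5.4, Study Drug Preparation.** A stock syringe ("12 mL, 0.16 mg/mL) will be available for the addition to the 2.8 L Perfadex bag") is thawed, and adding its contents "will achieve a final concentration of 0.69 mg/L of solution (i.e., 10 uMolar or 1.93 mg for each 2.8 liter bag").

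Section 5.4 assigns the weaker of its two stocks to this use: "The first stock solution will be a 12 mL (0.16mg/mL) stock solution to be used in the Perfadex preservation solution" and the pneumoplegia solutions. Both stocks are made from the commercial product, "Hope Pharmaceuticals, Sodium Nitrite Injection USP (30mg/mL"). Under Organ Implantation Prior To Reperfusion, section 5.4 pairs 10 uMolar with 0.69 mg/L again, this time for the pneumoplegia solution.

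**The concern.** The bag, the numeral and the molar label are the same in both sections, but one gives milligrams per millilitre and the other milligrams per litre. Section 5.5 describes what is infused into the donor lung and can be read without 5.4. A reader who does so finds a mass concentration and a molar concentration that disagree, with nothing to choose between them. A team member who checks a bag against 5.5 would be checking it against a contradictory specification.

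The primary objective of the trial is safety, and this is the strength of the study drug. At stake is the clarity of a dosing instruction. The endpoints, sample size and analysis do not depend on it.

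**Working it through.** **Inputs.** From 5.4: syringe 12 mL at 0.16 mg/mL; bag 2.8 L; final concentration 0.69 mg/L, equated with 10 uMolar and 1.93 mg per bag; commercial product 30 mg/mL. From 5.5: final concentration 0.69 mg/mL, also labelled 10 uMolar, in 2.8 L bags.

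**1. Reproduce the figures in 5.4.**
- Mass in the syringe = volume × strength = 12 mL × 0.16 mg/mL = 1.92 mg.
- Concentration in the bag = 1.92 mg / 2.8 L = 0.686 mg/L, or 1.92 / 2.812 = 0.683 mg/L if the added 12 mL is counted.
- Mass implied by the stated concentration = 0.69 mg/L × 2.8 L = 1.932 mg.
- On the section's own pairing (0.69 mg/L = 10 uMolar), the syringe gives 10 × 0.686/0.69 = 9.9 uMolar, and also 9.9 with 0.683.

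The figures in 5.4 agree with one another within rounding.

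**2. Apply the same arithmetic to 5.5.**
- Mass per bag = 0.69 mg/mL × 2,800 mL = 1,932 mg.
- Ratio to 5.4 = 1,932 / 1.932 = 1000.
- 0.69 mg/mL = 690 mg/L. On the pairing in 5.4 this is 10 × 690/0.69 = 10,000 uMolar, against the 10 uMolar printed in the same sentence.

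No molar mass from outside the documents is needed, because the pairing comes from the protocol.

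**3. Can the assigned stock reach the figure in 5.5?**
- 0.69 / 0.16 = 4.3. The final solution would have to be 4.3 times as strong as the stock added to it. Dilution cannot do this, however many syringes are used.
- The 30 mg/mL product could reach it: 1,932 / 30 = 64.4 mL per bag, or 1,932 / (30 − 0.69) = 65.9 mL if the added volume is counted. Section 5.4 does not assign the product to Perfadex in that form.

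**4. Scale.** The recipient infusion in 5.4 uses one syringe "to prepare a 40 mg Sodium Nitrite in a 250 ML infusion" bag. 1,932 / 40 = 48.3. This compares amounts of drug only. The bag flushes a procured lung, 5.5 leaves the volume used to the surgical team, and the documents do not say how much would reach the recipient.

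**The case against.** The best reply is that this is one mistyped unit and not two competing intentions. Both sections state the same molar target, and 5.5 prints it directly after the disputed figure. Section 5.4 gives a mutually consistent set of numbers for the bag, and the pneumoplegia text repeats its pairing. Section 5.5 cannot be used alone to make up a bag, because it gives no amount to add; the concrete step is in 5.4, where a labelled, pharmacy-prepared syringe is emptied into the bag. The assigned stock cannot produce the higher strength, and the other prepared syringe holds only 1.33 mL × 30 mg/mL = 39.9 mg, so about 48 would be needed. Section 5.5 adds a further safeguard: "A member of the study team will be present for monitoring of this procedure".

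Most of this stands. It makes a literal 1000-fold error unlikely, and it makes the comparison with 40 mg an indication of scale, not of exposure. It does not remove the contradiction. Section 5.5 does not mention the syringe, and its description of the additive is close to the name of the 30 mg/mL product, the one strength in the plan that could reach the printed figure. Nothing in the text supplied for review expressly corrects 5.5.

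**Conclusion.** The concern holds. For one bag the protocol states two mass concentrations that differ exactly 1000-fold (1,932 mg and 1.93 mg per bag), and the sentence in 5.5 is also inconsistent with its own molar label. The probability of harm is low. The correction is still required, because the text is a study-drug strength in the administration section.

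The conclusion rests on the printed units and on the protocol's own pairing of 10 uMolar with 0.69 mg/L. Two limits apply. Some pages were not available, so a correction there cannot be ruled out. A text-extraction fault is improbable in running prose but should be excluded by looking at the source page. No view is taken on which strength is right.

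**What to change.** The sponsor and the pharmacy should reconcile the two sections so that both give one concentration, in one unit, with the mg per 2.8 L bag. Section 5.5 should also name the prepared syringe that is to be added. The bag label and the pharmacy worksheet should be checked against the agreed text. This costs a one-line wording amendment and that check, with no change to design, sample size or analysis.

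A separate, minor point can be tidied in the same amendment. Section 4.3.4 describes earlier human studies as "at doses much higher than the 40 mg dose planned for this trial", whereas section 8.1 puts the doses used at about 40 mg in one place and at 30 mg in another. The documents do not show that these statements refer to the same people. A few sentences drawn from the prior-study records should say which doses each group received. The need to correct 5.4 and 5.5 does not depend on this point.
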